#### 7.1.13 Handling of Dropouts or Missing Data

Missing data is expected to be minimal; however, there is a chance that some subjects will not have full, complete data for the entire analysis. Missing data for efficacy assessments will be imputed using the Last Observation Carried Forward (LOCF) approach. In conjunction, Observed Case data, reported data without imputation, will also be analyzed to assess the sensitivity of the analysis to the choice of imputation approach.

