#### 7 STATISTICAL METHODS

#### 7.1 Statistical and Analytical Plans

#### 7.1.1 General Considerations

For the purposes of this protocol, osteoarthritis of the knee outcomes will be examined. The hypothesis to be tested is to confirm that the use of micronized dHACM offers a

Page 11 of 27

[figure not shown]
statistically significant advantage over 0.9% normal saline solution placebo for the treatment of osteoarthritis of the knee.

All statistical tests will be two-sided and will be performed at the significance, unless otherwise stated. Note that a penalty will be applied due to performing 2 planned interim analyses (see Section 7.1.11 for more details). Continuous data will be summarized by randomized Active and Control groups using descriptive statistics (number, mean, median, standard deviation [SD], minimum, and maximum). Categorical data will be summarized by randomized Active and Control groups using frequency tables (frequencies and percentages).

In addition to the efficacy analyses at the time point specified in the primary, secondary, and exploratory efficacy analyses, all efficacy parameters collected at various time points during the study will also be presented.

All analyses and summaries will be generated using SAS (SAS Institute, Inc., Cary, North Carolina).

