#### 7.1.3 Co-Primary Efficacy Analysis

This study consists of co-primary efficacy endpoints, which requires both endpoints to demonstrate success at 2-sided, level of significance.

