#### 7.1.3.1 VAS Score for Pain Analysis (90 Days)

[figure not shown]
ANOVA on the change in VAS score for pain between baseline and 90 days with treatment as a fixed effect and study site as the block effect will be used to compare the efficacy between Active and Control groups at 2-sided, level of significance.

In the case of data not being normally distributed, nonparametric tests, such as Wilcoxon Rank Sum test, will be utilized to assess the treatment efficacy.

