### 7.1.3.2 Total WOMAC Score Analysis (90 Days)

Page 13 of 27

Page 14 of 27

[figure not shown]
ANOVA on the change in Total WOMAC score between baseline and 180 days with treatment as a fixed effect and study site as the block effect will be used to compare the efficacy between Active and Control groups at 2-sided, level of significance.

In the case of data not being normally distributed, nonparametric tests, such as Wilcoxon Rank Sum test, will be utilized to assess the treatment efficacy.

[figure not shown]

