#### 7.1.12 Multiple Comparisons / Multiplicity

There will be one interim analysis conducted when the study population reaches 50% of the total expected and a second interim analysis conducted after all subjects have completed the 180-day visit. Type I error will be adjusted for the interim analyses as mentioned in Section 7.1.11. Furthermore, one final analysis will be conducted upon study completion, which should mitigate any concerns of multiplicity.

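### LOCF is the visible rule for missing efficacy scores; a mixed model with a required tipping-point analysis would be a cheap improvement

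*SAP*

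**What the plan says.** SAP 7.1.13 sets the rule: "Missing data for efficacy assessments will be imputed using the Last Observation Carried Forward (LOCF) approach". It adds one check: "Observed Case data, reported data without imputation, will also be analyzed to assess the sensitivity of the analysis". It gives no dropout rate, only an expectation: "Missing data is expected to be minimal; however, there is a chance that some subjects will not have full, complete data".

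The visible analyses use a single time point. SAP 7.1.3.1 specifies "ANOVA on the change in VAS score for pain between baseline and 90 days with treatment as a fixed effect", with site as a block and a switch to a rank test if the data are not normal. The visible Total WOMAC text, which follows blank pages after heading 7.1.3.2, reads "ANOVA on the change in Total WOMAC score between baseline and 180 days with treatment as a fixed effect". The Statistical Methods paragraph of the protocol synopsis names the same ANOVA for Days 90 and 180. Success is joint (SAP 7.1.3): "This study consists of co-primary efficacy endpoints, which requires both endpoints to demonstrate success". The significance level is not visible, and SAP 7.1.1 says "Note that a penalty will be applied due to performing 2 planned interim analyses".

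SAP Sections 5, 7.1.2, 7.1.5, 7.1.11 and 7.3, and part of the text after 7.1.3.2, are blank in the public copy. A further missing-data check, or a rule that LOCF and Observed Case must agree, may stand there.

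**The concern.** Under LOCF a missing Day 90 or Day 180 score is replaced by an earlier one and analysed as if it had been observed. If scores are still improving and placebo subjects leave more often, more placebo subjects are held at a less improved value and the contrast tilts toward active. If active subjects leave more often, it tilts the other way. Even with equal dropout, an effect that grows with time is diluted.

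Observed Case is a useful comparison, but it can itself be biased when response-related dropout differs by arm. A gap between the two analyses does not show which is nearer the truth. Nothing visible probes dropout that depends on the unseen score.

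The joint success rule keeps false success low when neither endpoint responds. If one endpoint truly responds, the inflated error rate of the other becomes the trial's rate. The SAP introduction says the Day 90 and Day 180 results will guide Phase 3 planning, so bias in the estimate matters as well as type I error.

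**Working it through.** **Inputs from the documents.** About 466 subjects randomized 1:1 (protocol synopsis, Sample Size), so 233 per arm. Scores are taken at baseline and Days 30, 60, 90 and 180 (Procedures and Assessments). Tests are two-sided and both endpoints must succeed.

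**The plan's own figure.** The 466 cannot be rebuilt, because alpha, power, effect and SD are not visible. Working backwards at two-sided 0.05, the detectable effect is (1.96 + 0.84) × √(2/233) = 0.26 SD at 80% power and (1.96 + 1.28) × √(2/233) = 0.30 SD at 90%.

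**Assumed throughout.** VAS SD 25 mm, so SE = 25 × √(2/233) = 2.32 mm; alpha 0.05. Improvement is a negative change.

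**Step 1: closed form, no true effect.** Let dropout proportion d split evenly before Days 30, 60 and 90, with baseline carried forward if nothing later exists. The carried mean is m = (0 + μ30 + μ60)/3, and the LOCF bias (active minus placebo) is (d_placebo − d_active) × (μ90 − m).

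- Path −15/−20/−24 mm: m = −11.67 and μ90 − m = −12.33. For 10% vs 5% (placebo vs active) the bias is 0.05 × −12.33 = −0.62 mm (single-endpoint type I error 5.8%). For 20% vs 10% it is −1.23 mm (8.3%).
- Path −10/−20/−30 mm: μ90 − m = −20. The same gaps give −1.0 mm (7.2%) and −2.0 mm (13.9%).
- Equal dropout: zero.

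**Step 2: simulation of both endpoints.** 8000 trials per scenario, no site effect. Mean change at Days 30/60/90 is −10/−16/−20 mm (VAS) and −9/−14/−18 points (Total WOMAC, SD 18). Visit correlation is AR(1) 0.7 and VAS–WOMAC correlation 0.7. Dropout occurs after Day 30 or Day 60, logistic with slope 0.8 per SD of the last VAS change, with intercepts set to give the missing rates. No true effect:

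| Placebo vs active missing | 5% vs 3% | 10% vs 5% | 20.6% vs 8.8% |
|---|---|---|---|
| LOCF bias toward active, mm | 0.3 | 0.7 | 1.6 |
| Same, divided by SE 2.32 | 0.13 | 0.30 | 0.69 |
| Observed Case bias against active, mm | 0.2 | 0.6 | 1.4 |
| Mixed-model bias, mm | ≤0.02 | ≤0.02 | ≤0.02 |
| False success on both, LOCF | 1.2% | 2.0% | 4.3% |
| Range over repeat runs, LOCF | 0.8–1.3% | 1.7–2.1% | 4.3–5.0% |
| False success, mixed model | 0.8% | 0.9% | 0.7% |
| False success, LOCF and Observed Case both required | 0.6% | 0.4% | 0.1% |

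Full data give 0.5 to 0.8% (up to 1.0% in a smaller repeat run). At alpha 0.025, LOCF gives 0.6%, 1.0% and 2.1% against 0.2 to 0.4%. Monte Carlo SE is about 0.01 mm for bias and 0.1 to 0.2 percentage points for joint false success.

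**Step 3: VAS responds, WOMAC does not.** At the first two gaps, false success is 3.7% and 5.0% with LOCF, 2.8% and 2.6% with full data, 2.6% and 2.5% with the mixed model, and 2.2% and 1.6% if LOCF and Observed Case must both win.

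**Step 4: other dropout patterns.**

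- Unrelated to response, same three gaps: LOCF errs 0.1, 0.4 and 0.8 mm toward active (joint false success 1.0%, 1.4%, 2.8%). Observed Case and the mixed model are unbiased.
- Same response-related rule in both arms, 5% or 15% missing: no bias in any method.
- Early-peaking course (−22/−21/−20 mm), largest gap: LOCF errs 0.5 mm toward active if dropout is response-related, 0.2 mm the other way if unrelated.

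**Step 5: power.** True late effect −2/−5/−8 mm and −1.5/−4/−6 points, equal unrelated dropout. LOCF loses 0.2 mm at 5% missing and 0.7 mm at 15%. Power on both endpoints:

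| Missing | Full data | Mixed model | Observed Case | LOCF | LOCF and Observed Case both |
|---|---|---|---|---|---|
| 5% | 90% | 88.9% | 88.3% | 87.7% | 85.8% |
| 15% | 90% | 86.7% | 84.3% | 83.0% | 79.4% |

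**Step 6: dropout driven by the unseen Day 90 score.** The ranking reverses. Across runs the mixed model errs 0.3, 0.6–0.7 and 1.5–1.6 mm against active, and LOCF at most 0.02, 0.12 and 0.44 mm. With the gaps reversed (active missing more), the mixed model errs 0.3, 0.6 and 1.5 mm toward active. Its joint false success is 1.2%, 1.6% and 3.1%, against 1.0%, 0.8% and 0.5% for LOCF. The shift in missing scores that removes this bias is bias divided by missing gap: VAS 0.61/0.049 and 1.49/0.119, both about 12.5 mm; WOMAC 0.31/0.049, about 6 points.

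**The case against.** The strongest reply is that unequal dropout is assumed. The SAP expects little missing data, the primary endpoint falls 90 days after one blinded injection, and the only cause of disruption the visible text names is COVID-19, which there is no visible reason to expect to differ by arm. Within that range the bias is 0.13 to 0.30 SE, and if neither endpoint responds, joint false success stays at or below about 2.1%, under the 2.5% directional level. This stands. It limits the priority of the point and gives the 20.6% vs 8.8% gap little weight.

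Second, the plan already has a working check. With no true effect, a win on both LOCF and Observed Case was never inflated. With unequal dropout and improving scores, zero bias lay between the two or within 0.03 mm of the nearer one. The disposition tables in SAP 7.1.7 should also help show unequal dropout. This stands too, but requiring agreement costs more power than a mixed model, and no such requirement is visible. SAP Section 5 on success criteria is blank and could hold one.

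Third, the mixed model can be worse than LOCF (Step 6). That is true, and it is why the tipping-point analysis must be required. Observed Case does not cover that case: a repeat run put it 0.95 and 2.20 mm off at the two larger gaps.

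Fourth, the simulation suits the mixed model: normal data, equal covariance, and a correlation structure that makes WOMAC missing at random although VAS drives dropout. With a shared-factor correlation, mixed-model WOMAC bias was 0.05, 0.13 and 0.30 points, still below LOCF's 0.13, 0.31 and 0.79. Skewed data and Day 180 were not simulated.

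**Conclusion.** The point holds as a worthwhile improvement, with medium confidence; it is not a fatal flaw. LOCF is the visible rule. Under response-related dropout at 5% vs 3% or 10% vs 5%, it shifts the VAS contrast by 0.3 to 0.7 mm and adds roughly one to two and a half percentage points to false success when one endpoint responds and the other does not. With equal dropout and a late effect, it gives up 1.2 points of joint power to a mixed model at 5% missing (88.9 − 87.7) and 3.7 points at 15% (86.7 − 83.0).

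These figures rest on assumed dropout, SDs, correlations, mean courses and alpha, none of which the documents supply. No visible text shows that dropout will differ by arm. If missing data are minimal, the effect is small. With no true effect and the same dropout rule in both arms, it is nil.

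**What to change.** In SAP 7.1.13, and in matching text in 7.1.3 and the protocol synopsis:

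1. Make the main analysis of the Day 90 and Day 180 endpoints a mixed model for repeated measures on change at Days 30, 60, 90 and 180. Include treatment-by-visit and site, use an unstructured covariance, and use data up to any open-label injection. State what replaces the switch to a rank test.
2. Require multiple imputation with a delta (tipping-point) shift set separately by arm. Prespecify a grid that reaches past the Step 6 shifts, for example 0 to 25 mm for VAS and 0 to 18 points for Total WOMAC (one assumed SD each). Say beforehand which tipping shifts would undermine the result. For scale, an observed 8 mm benefit has 8 − 1.96 × 2.32 = 3.46 mm to spare. With 10% of the active arm missing, those subjects would have to be about 35 mm worse than modelled to lose significance; with 20% missing, about 17 mm.
3. Keep LOCF and Observed Case as supportive, and state how disagreement will be read.

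Make the change before any unblinded comparative look. SAP 7.1.12 says "There will be one interim analysis conducted when the study population reaches 50% of the total expected", and whether that look compares arms is not visible. If such a look has already taken place, leave the main analysis alone and add items 1 and 2 as sensitivity analyses, documented as added after the look.

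The cost is SAP wording, matching protocol text and modest programming; the visits are already scheduled. The drawback is reliance on missing at random, which item 2 is there to test.

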#### 7.2 Safety Evaluation

The safety endpoint of this study is the proportion of product-related AEs, SAEs, and unanticipated adverse events throughout the study in the micronized dHACM versus placebo-treated group. All enrolled subjects who receive at least one injection will be

Page 22 of 27

[figure not shown]
used for the analysis of safety data. A listing of AE affected by the COVID-19 related study disruption will be presented.

The incidence of all treatment emergent adverse events and serious adverse events as well as major complications (product related) will be compared between the two treatment groups. Safety will also be reported as the frequencies of occurrence of each adverse event, the rate of adverse events per subjects/year and time to each event. In addition, the number of subjects with each serious adverse event type will be reported.

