
Name of Investigational Product: Allogeneic Micronized Dehydrated Human Amnion/Chorion Membrane (Micronized dHACM), a.k.a. AmnioFix Injectable
 
Study Design: A Phase 2B, Prospective, Double-Blinded, Randomized Controlled Trial of the Micronized dHACM Injection as Compared to Saline Placebo Injection in the Treatment of Osteoarthritis of the Knee
 
Indication: Knee osteoarthritis (OA)
 
Objective: To determine the safety and effectiveness of micronized dHACM as compared to the 0.9% Sodium Chloride Injection, USP placebo control for the treatment of knee osteoarthritis
 
Sample Size: Approximately 466 subjects will be enrolled in this study. Subjects to be randomized 1:1 in treatment arms.
 
Study Plan: The estimated enrollment period is 26 months. Each subject will receive 1 injection and be evaluated for efficacy and safety during a 12-month observation period. A second injection (open-label access to micronized dHACM) will be offered to all subjects at the 180-day, 270-day, and 365-day time points, see open-label access section below; it may only be used once. The study is expected to be completed within 44 months, inclusive of enrollment and follow-up for all subjects.
 
Procedures and Assessments:
 
 • Treatment (approx. 1 day): Screening, pre-procedure evaluation, injection procedure, baseline evaluation. • Clinical Follow-up (365-545 days): Routine follow-up with physical examination; pain, function, and quality of life measurements: Visual Analog Scale (VAS) for Pain, VAS for Satisfaction, Western Ontario and McMaster Universities (WOMAC) osteoarthritis index, and Knee injury and Osteoarthritis Outcome Score (KOOS) will be evaluated at baseline, 30 days, 60 days, 90 days, 180 days, 270 days and 365 days after the initial treatment, and at time of open-label access and 30 days, 60 days, 90 days, and 180 days following the second injection should the subject elect to receive the open-label access treatment. Subject pain diaries will be completed at predefined intervals. • Safety Follow-up (365-545 days): Adverse Events (AEs), Serious Adverse Events (SAEs), and Unanticipated Adverse Events will be evaluated at 30 days, 60 days, 90 days, 180 days, 270 days and 365 days after the initial treatment, and at time of open-label access and 30 days, 60 days, 90 days, and 180 days following the second injection should the subject elect to receive the open-label access treatment. 
Primary Efficacy Endpoints (VAS for Pain and Total WOMAC): The co-primary efficacy endpoints are:
 
 • The change in VAS score for pain between baseline and Day 90 • The change in WOMAC osteoarthritis index total score (Total WOMAC score) between baseline and Day 90 
Primary Safety Endpoint: The primary safety endpoint is the proportion of product-related Adverse Events (AEs), Serious Adverse Events (SAEs), and unanticipated adverse events throughout the study.
 
Secondary Endpoints: The secondary efficacy endpoints for this study are:
 
 • Change in VAS score for pain between baseline and 180 days • Change in Total WOMAC score between baseline and 180 days

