
Exploratory Endpoint:

For the cohort of subjects in the main phase of the study, i.e. who did not receive or have not yet received an open-label injection, the following exploratory endpoints will be assessed:

- Change in VAS score for pain between baseline and i-day (with i=30, 60, 270, and 365 days)
- Change in Total WOMAC score between baseline and i-day (with i=30, 60, 270, and 365 days)
- Change in pain, stiffness, and physical function WOMAC subscale scores between baseline and i-day (with i=30, 60, 90, 180, 270, and 365 days)
- Change in VAS score for satisfaction between baseline and i-day (with i=30, 60, 90, 180, 270, and 365 days)
- Change in KOOS scores between baseline and i-day (with i=30, 60, 90, 180, 270, and 365 days)
- Patient pain diary endpoints will be collected and summarized across applicable time points

For the cohort of subjects in the extension phase, i.e. who received the open-label injection and are within the period after the open-label injection, the following endpoints will be collected and summarized across applicable time points: VAS score for pain, Total WOMAC, WOMAC subscales for pain, stiffness and physical function, VAS score for satisfaction, KOOS, and pain diary entries.

Inclusion Criteria

All subjects enrolled must meet all the following criteria:

1. Age \geq 21 and \leq 80 years
2. Subject has a diagnosis of osteoarthritis (OA) defined as Grade 1 to 3 on the Kellgren Lawrence grading scale
3. Subject is willing and able provide informed consent and participate in all procedures and follow-up evaluations necessary to complete the study
4. Subject must have a VAS pain scale greater than 45

Exclusion Criteria

Any potential subjects meeting any of the following criteria will be excluded from enrollment and subsequent randomization.

1. Subject has a diagnosis of osteoarthritis (OA) defined as Grade 4 on the Kellgren Lawrence grading scale
2. BMI greater than 40 kg/m²
3. Subject has active infection at the injection site
4. Symptomatic OA of the contralateral knee or of either hip that is not responsive to acetaminophen (Tylenol®) and requires other therapy.
5. Subject has rheumatoid arthritis, psoriatic arthritis, or have been diagnosed with any other disorders that is the primary source of their knee pain, including but not limited to: osteonecrosis, radiculopathy, bursitis, tendinitis, tumor, cancer
6. Subject has documented history of gout or pseudo-gout

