7. Subject has autoimmune disease or a known history of having Acquired Immunodeficiency Syndromes (AIDS) or HIV
8. Subject has received any of the following to the target knee:
 - a. Intra-articular hyaluronic acid (HA) injection within 12 weeks prior to screening
 - b. Steroid or platelet rich plasma (PRP) injection within 12 weeks prior to screening
 - c. Has had or is planning to have major surgery or arthroscopy in the target knee within 26 weeks of treatment
 - d. History of a total knee arthroplasty
9. Subject has used an investigational drug, device or biologic within 12 weeks prior to treatment
10. Subject has a history of immunosuppressive or chemotherapy in the last 5 years
11. Subject has had prior radiation at the site
12. Subject is currently taking anticoagulant therapy (excluding Plavix or Aspirin)
13. Subject is pregnant or plans to become pregnant within 365 days of treatment
14. Subject has any significant medical condition that, in the opinion of the Investigator, would interfere with protocol evaluation and participation
15. Subject is a worker's compensation patient
16. Subject is a prisoner

Open-Label Access:

All study subjects will be eligible to receive one injection of micronized dHACM at either of the Day 180, Day 270, and Day 365 time points. The investigators and subjects will remain blind to the initial treatment assignment at this time, and until the study is unblinded.

Subjects who receive the open-label access treatment will continue to be followed for 180 days after this second injection, regardless of the time at which treatment was received.

Statistical Methods:

The change in VAS score for pain and Total WOMAC score between baseline and Day 90 (primary endpoints) and between baseline and Day 180 (secondary endpoints) will be compared between the treatment arms using an ANOVA with treatment as a fixed effect and study site as the block effect.

For the purposes of this protocol, we will be examining knee osteoarthritis. The hypothesis to be tested is to confirm that the use of micronized dHACM offers a statistically significant advantage over placebo control.

Efficacy and safety data will be submitted for evaluation following the completion of the study follow-up.

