#### **TABLE OF TABLES**

#### **TABLE OF FIGURES**

This Statistical Analysis Plan (SAP) is intended to act as an outline for the statistical interpretation of the data resulting from the Phase 2B Investigational New Drug (IND) trial, titled: "A Phase 2B, Prospective, Double-Blinded, Randomized Controlled Trial of the Micronized dHACM Injection as Compared to Saline Placebo Injection in the Treatment of Osteoarthritis of the Knee." Specific questions regarding this trial's design and/or implementation may be addressed by the study protocol (AIOA001 Protocol V2).

This study consists of two phases – Main Phase and Open-Label Extension Phase (Extension Phase). The Main Phase of the study includes subjects during the observation period where they received the randomized treatment only. The Extension Phase of the study includes the subjects who elected to receive an open-label injection of micronized dHACM injection at either of the 180-day, 270-day or 365-day visits, during the 180-day period following the open-label injection.

In order to facilitate the planning of a Phase 3 pivotal study based on results of the primary and secondary efficacy parameters at 90-day and 180-day, the randomized treatment for the Main Phase will be unblinded and a snapshot of the database will be taken after all randomized subjects completed the 180-day assessment. Formal database preparation process will be performed to ensure the integrity and quality of the database and an interim analysis of the primary and secondary efficacy endpoints as well as the exploratory efficacy endpoints up to the 180-day time point will be performed. At the end of the study, the database will be locked. The database lock process will be performed to ensure the integrity and quality of the database; and formal analyses will be performed.

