#### 2.2 Primary Safety Endpoint

The primary safety endpoint is the proportion of product-related Adverse Events (AEs), Serious Adverse Events (SAEs), and unanticipated adverse events throughout the study.

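### As visibly written, the primary safety comparison runs on into the period when both arms may receive open-label dHACM, so its result depends on open-label uptake

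*SAP*

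**What the plan says.** The whole-study window appears in three places. The protocol synopsis (Primary Safety Endpoint) and SAP 2.2 both count product-related AEs, SAEs and "unanticipated adverse events throughout the study". SAP 7.2 turns this into a between-group contrast: the "proportion of product-related AEs, SAEs, and unanticipated adverse events throughout the study in the micronized dHACM versus placebo-treated group".

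The protocol's Open-Label Access section states: "All study subjects will be eligible to receive one injection of micronized dHACM at either of the Day 180, Day 270, and Day 365". Subjects who take it "will continue to be followed for 180 days after this second injection". The Safety Follow-up entry in the synopsis reads "365-545 days): Adverse Events (AEs), Serious Adverse Events (SAEs), and Unanticipated Adverse Events will be evaluated", and lists assessments after the second injection as well as after the first.

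The SAP introduction separates two periods. Of the first it says: "The Main Phase of the study includes subjects during the observation period where they received the randomized treatment only". The second, which covers the 180 days after the elective injection, is described in these terms: "The Extension Phase of the study includes the subjects who elected to receive an open-label injection of micronized dHACM injection". The protocol uses this split for its exploratory efficacy endpoints, whose main-phase cohort consists of subjects "who did not receive or have not yet received an open-label injection". SAP section 4 makes endpoints after Day 180 exploratory because of the treatment change, but it does so under the effectiveness objectives.

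The visible part of SAP 7.2 takes everyone with at least one injection as the safety population. It compares incidence between the two treatment groups and adds event rates per subject-year and time to event. It names no phase, no cut at the open-label injection, and no rule for assigning events that follow it. SAP 7.1.1 summarises categorical data by randomised group.

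**The concern.** The plan recognises for efficacy that treatment changes from Day 180, yet its visible safety text keeps the whole-study window for a comparison of dHACM with placebo. If events are counted by randomised arm, a product-related event after open-label dHACM in a placebo subject counts against placebo, and an Active subject can contribute events from two dHACM injections. The contrast is then no longer dHACM versus saline. It is a mixture whose composition is set by how many subjects in each arm choose the second injection.

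Two features of the plan might seem to prevent this, but do not. Restricting to product-related events does not help, because an event caused by open-label dHACM is product-related whatever the randomised arm. Rates per subject-year and time to event deal with unequal follow-up, but not with crossover unless they are cut at the second injection.

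At stake is how the main safety result of a Phase 2B trial is read: a true excess on dHACM could look smaller or larger than it is.

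**Working it through.** **1. Is the open-label period inside the safety window?** Latest open-label visit, Day 365, plus 180 days of follow-up = 545. This reproduces the upper end of the protocol's 365-545 days exactly, so it is.

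**2. How much follow-up is affected?** Assume 50% uptake.
- All at Day 180: Main Phase 0.5×180 + 0.5×365 = 272.5 days per subject; Extension 0.5×180 = 90; share 90/362.5 = 25%.
- All at Day 365: 90/(365 + 90) = 90/455 = 20%.

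**3. Effect on the contrast, counted by randomised arm.** The endpoint is read as the proportion of subjects with at least one product-related event. Let p1 be the risk per dHACM injection, p0 the risk after saline, and uA and uP the open-label uptake in Active and placebo. Risks are taken as independent between injections.
- Active = 1 − (1 − p1)(1 − p1·uA)
- Placebo = 1 − (1 − p0)(1 − p1·uP)

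The documents give none of these values. Assume p1 = 10% and p0 = 4%: true ratio 2.5, true difference 6.0 points.

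| Uptake Active/placebo | Active | Placebo | Ratio | Difference (points) |
|---|---|---|---|---|
| none | 10.0% | 4.0% | 2.50 | 6.0 |
| 50/50 | 1 − 0.90×0.95 = 14.5% | 1 − 0.96×0.95 = 8.8% | 1.65 | 5.7 |
| 30/60 | 1 − 0.90×0.97 = 12.7% | 1 − 0.96×0.94 = 9.8% | 1.30 | 2.9 |
| 60/20 | 1 − 0.90×0.94 = 15.4% | 1 − 0.96×0.98 = 5.9% | 2.60 | 9.5 |

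Other assumed risks show the same pattern at 50/50. With 10%/5% the ratio goes from 2.00 to 1.49 and the difference from 5.0 to 4.75 points. With 20%/10% the ratio goes from 2.00 to 1.47 and the difference from 10.0 to 9.0. Equal uptake mainly dilutes the ratio; unequal uptake moves both measures.

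**4. No true difference.** With 5% in both arms and 30/60 uptake: Active 1 − 0.95×0.985 = 6.4%, placebo 1 − 0.95×0.97 = 7.9%, ratio 0.82 where the truth is 1.0.

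**5. Does attribution by treatment received cure it?** Not with the subject as the unit. At 10%/4% and 50/50, dHACM = (0.145 + 0.5×0.10)/(1 + 0.5) = 13.0% against 4.0%: ratio 3.25 where the truth is 2.5, because Active subjects may have two dHACM injections to count.

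**6. Does a crude Main Phase proportion cure it?** No. Assume a constant hazard, 5% risk over 365 days in both arms, and all open-label use at Day 180. The 180-day risk is 1 − 0.95^(180/365) = 2.50%. At 30/60 uptake:
- Active: 0.7×5% + 0.3×2.50% = 4.25%
- Placebo: 0.4×5% + 0.6×2.50% = 3.50%
- Ratio 1.21 where the truth is 1.0, because the arm with more takers is observed for less time.

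Over the window to Day 180, both arms give 2.50% and ratio 1.0 at any uptake.

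**The case against.** The strongest objection is that much of the SAP is not visible. Section 7.1.2 (Analysis Set), where a safety set by phase would normally be defined, shows only its heading. Sections 5, 6, 7.3 and 7.4 are also empty, and a figure is missing within 7.2. The SAP introduction defines the two phases for the whole study, not only for efficacy. A reader might infer that the plan has no phase rule for safety; the documents do not support that, and this part of the objection stands. What remains is that three visible statements set the whole-study window, and none of them restricts it or points to a restriction.

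Counting by randomised arm is itself an inference from 7.1.1. The wording of 7.2 (placebo-treated, treatment-emergent) would also fit attribution by treatment received. That leaves the rule open, and step 5 shows that this reading does not give a clean contrast per subject.

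A reader might also infer that the comparison will reverse or conceal a true excess. That goes too far. With 8% and 4% assumed, reversal appears at 20/80 uptake (9.5% vs 10.1%, ratio 0.93), which is an extreme split. The protocol keeps subjects and investigators blind to initial assignment when open-label access is offered, which makes such splits less likely, although blinding does not force uptake to be equal. At equal uptake the risk difference hardly moves.

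Finally, the visible text sets no safety hypothesis, margin or decision threshold, and events could be split by date at reporting. Both points are fair and limit the severity. They do not justify leaving the stated primary window as it is.

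**Conclusion.** The concern holds for the plan as visibly written. The primary safety contrast covers a period in which both arms may receive open-label dHACM, and the visible safety text does not apply the SAP's own phase split. Counted by randomised arm, the risk ratio is generally diluted at equal uptake where a true excess exists (2.5 to 1.65 at 50/50 under 10%/4%), while the risk difference barely changes (6.0 to 5.7 points). Both shift when uptake differs between arms.

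These figures show dependence on uptake, not its actual size: event risks and uptake are assumed, and risks are treated as independent per injection. The conclusion also depends on there being no phase rule for safety in text not visible here, so confidence is medium. A reader might conclude that restricting the proportion to the Main Phase is enough. Step 6 shows that it is not when risk accrues over time; it would be harmless only if events cluster soon after injection, which the documents do not establish. The point should be fixed, but it does not invalidate the trial's safety data.

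**What to change.** If a section not visible here already sets a phase and attribution rule for safety, cite it in SAP 2.2 and 7.2. Otherwise amend those sections and the protocol synopsis as follows:

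- **Primary comparison of proportions:** events from the first injection up to the Day-180 visit and before any open-label injection. This is an equal planned window in which no one has crossed over.
- **Supporting analyses:** Main Phase subject-year rates and time to event, censored at the open-label injection, with a note that this censoring may be informative because the injection is elective. Do not use a crude Main Phase proportion as the primary contrast.
- **Extension Phase:** report events separately by sequence (placebo then dHACM, dHACM then dHACM), with person-time split at the second injection.
- **Whole study:** keep full listings of all events.

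The cost is wording plus a date-based phase flag in the adverse-event dataset; no new data are needed. The drawback is that the primary proportion omits uncrossed time after Day 180. At 50% uptake this is 92.5/272.5 = 34% of Main Phase days if all open-label use is at Day 180, and 185/365 = 51% if all is at Day 365. The censored rates and the listings still report that time.
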